2.1 Study Rationale

The current approach to anti-inflammatory controller therapy in asthma is based on a step-wise intensification of a daily maintenance regimen primarily centred around inhaled corticosteroids (ICS) and leukotriene receptor antagonists (LTRAs), with the addition of long-acting β_2 agonists (LABAs) in patients with more severe asthma (NAEPP 2020; GINA 2020). Approximately 5% to 10% of persons with asthma have a severe form of disease that is usually managed with high-dose inhaled glucocorticoids (GCs) and bronchodilators (BDs; Bateman et al, 2010; Chung et al, 2014). Within this group, 12% to 45% of persons rely on frequent or maintenance use of oral GC (oral corticosteroids [OCS]) therapy (Moore et al, 2007; Shaw et al, 2015; Miloslavsky et al, 2017). Biologics targeting interleukin (IL)-5, IL-5R, IL-4R, and immunoglobulin E (IgE) are now included in international treatment guidelines as an add-on treatment to patients uncontrolled with ICS/LABA treatment (GINA 2020).

Although OCS therapy can be effective at treating several inflammatory diseases, it adversely affects health-related quality of life (Swedin et al, 2017; Sweeney et al, 2016) and is associated with several side-effects, including osteoporosis, hypertension, and depression (Dinsen et al, 2013). Long-term use of OCS suppresses the hypothalamic pituitary-adrenal (HPA) axis and prevents cortisol production (Neogi et al, 2010; Nicholas et al, 2018). Upon withdrawal of OCS, restoration of the HPA axis may take a longer time, thus leading to

adrenal insufficiency (AI) in approximately 50% of patients (Dinsen et al, 2013). Symptoms and signs of AI are often nonspecific and can include fatigue and nausea; moreover, impairment of the cortisol-induced stress response can be life-threatening (adrenal crisis) in physiologically traumatic situations such as during surgery, bodily injury, or severe systemic infections (Alves et al, 2008; Dinsen et al, 2013; Johnson et al, 2014; Joseph et al, 2016). It is therefore important to screen and monitor patients for AI while down-titrating their OCS dose, especially once the patient has reached a physiological dose, which is defined as approximately 5 mg per day of oral prednisone (Alves et al, 2008).

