At the IPD Visit the participants will be given the following 3 options as to how they will be followed:

- 1. The participant should be encouraged to return for all regular clinic visits and perform all scheduled assessments (excluding IP administration) until the EOT visit at Week 52 (± 5 days).
- 2. The participant will be offered follow-up on a monthly basis via telephone calls while continuing ePRO data collection on the handheld device at home (no further procedure will be performed) until the participant completes the on-site EOT visit at Week 52 (± 5 days).
- 3. If the participant cannot or does not wish to comply with any of the options above (or any component of them such as only telephone-based visits without completion of the ePRO data), the investigator will contact the participant via telephone at 52 weeks after baseline. No other study assessments will be performed prior to this contact.

Participants who discontinue IP with option 1 or 2 are allowed to further reduce their OCS dose following the same protocol-specified OCS dose reductions scheme as participants being still on-treatment.

If the last study intervention administration was after Week 36 for options 1 or 2, the participant will return to the clinic for an EOT visit at Week 52 (\pm 5 days). For option 3, the investigator will contact the participant at 52 weeks post baseline.

If a participant chooses option 1, all assessments will be completed as per the SoA as indicated in Table 1. If a participant chooses option 2 or 3, the key information to be collected during the telephone calls are AESIs/DAEs/SAEs, changes in concomitant medication, and asthma exacerbation information.

Participants who initially choose options 1 or 2 and subsequently cannot or do not wish to comply with the requirements of their option can continue with a less intensive option

(ie, participants initially choosing option 1 can continue with options 2 or 3, participants initially choosing option 2 can continue with option 3).

If a participant discontinues tezepelumab due to a study specific discontinuation criterion, this should always be recorded as 'Development of study specific discontinuation criteria' on the Discontinuation of IP form in the eCRF.

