8.1.2 OCS Dose Titration

At screening visit, participants will continue with or be switched to prednisone/prednisolone. For participants not previously receiving prednisone/prednisolone as OCS, the conversion table shown in Appendix D will be used to calculate the equivalent prednisone/prednisolone dose for dose titration.

The OCS dose titration in the reduction phase will be followed as per Table 7 depending on the initial OCS dose and HPA axis evaluation. Note: For participants who must reduce OCS dose more frequently than Q4W or if the scheduled dose reduction does not coincide with a clinic visit (see reduction scheme in Table 7), OCS dose reduction may occur remotely (eg, by telephone) instead of a clinic visit.

If Table 7 instructs to reduce dose by 5 mg increments, but the initial OCS dose is < 5 mg to the nearest dosing level, the 1st reduction would be smaller, rounding down to the nearest 5 mg, then continue on with 5 mg Q2W reductions (examples below):

- eg, $12.5 \rightarrow 10 \text{ mg} \rightarrow \text{etc.}$
- eg, $23 \rightarrow 20 \rightarrow 15 \rightarrow 10 \text{ mg} \rightarrow \text{etc.}$

• eg, $19 \rightarrow 15 \rightarrow 10 \text{ mg} \rightarrow \text{etc.}$

If Table 7 instructs to reduce the initial dose by 2.5 mg increments, but the initial dose is < 2.5mg to the next dosing level, the 1st reduction would be smaller, rounding down to the nearest 2.5 mg, then continue on with 2.5 Q4W reductions (examples below):

- eg, $8 \rightarrow 7.5 \rightarrow 5 \rightarrow \text{etc.}$
- eg, $6.25 \rightarrow 5 \rightarrow$ etc.

Investigators may also choose to slow the down-titration to 1 mg Q4W once the participant reaches an OCS dose of 5 mg/day based on participant symptoms.

For all participants, HPA axis integrity will be evaluated after 4 weeks on 5 mg/day and prior to tapering down the OCS dose (for participants with baseline OCS doses equal to 5 mg/day, this will be assessed 4 weeks after the first dose of tezepelumab administration and before initiation of the OCS reduction and maintenance phase). See Section 8.2.1 for details.

Table 7

OCS Dose Titration Schedule During the OCS Reduction and Maintenance Phase

Initial OCS	OCS down-titration to reach		an OCS dose of:		
dose/day					
	20 mg	10 mg	7.5 mg	5 mg	0 mg
> 20 mg	Reduction of 5 mg	Reduction of	2.5 mg of the	2.5 mg of the	No AI: reductions of 2.5 mg of the daily dose Q4W until reaching dose

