8.2.1 Hypothalamic-pituitary-adrenal Axis Evaluation

For all participants, HPA axis integrity will be evaluated after 4 weeks on 5 mg/day and prior to tapering down the OCS dose (for participants with baseline OCS doses equal to 5 mg/day, this will be assessed 4 weeks after the first dose of tezepelumab administration and before initiation of the OCS reduction phase).

First, a screening method with morning serum cortisol is done (8-9 am morning cortisol level), to evaluate whether the participant has:

- Normal cortisol levels (Table 9)
- Complete AI (Table 9).

Cortisol levels from the morning cortisol test that are below normal range and above the complete AI range are considered 'indeterminate' (Table 9), and require additional testing described below (for sites where tetracosactide is not available or not registered, please see Appendix M).

If the morning cortisol is in the indeterminate range, then the ACTH stimulation test is done within approximately 1 week (see Section 8.2.1.2 for details). The ACTH stimulation test is more specific than the morning cortisol test, and can determine whether the participant has:

- Normal cortisol levels: > 450 nmol/L (> 675 nmol/L for participants taking oestrogen-containing contraceptives)
- Complete AI: < 250 nmol/L (< 375 nmol/L for participants taking oestrogen-containing contraceptives)
- Partial AI: 250 to 450 nmol/L (375 to 675 nmol/L for participants taking oestrogen-containing contraceptives).

For morning serum cortisol and ACTH stimulation tests, hold OCS dose and other concomitant medications that could interfere with cortisol results as follows (see Section 6.5):

- The last OCS dose should be taken \geq 24 hours prior to testing
- Participants must not take ICS (or ICS/LABA if in single inhaler) treatment on the
 morning of the morning cortisol level/ACTH stimulation test (for participants taking a
 once-daily ICS/LABA formulation, eg, fluticasone furoate/vilanterol, participants must
 not take the treatment ≤ 24 hours prior to the morning of the morning cortisol
 level/ACTH stimulation test)
- If a participant requires a short course of macrolides, antivirals, or azoles, there must be a window of ≥ 1 week prior to the testing of cortisol levels.

The process will be as described in Figure 3.

[figure not shown]

Figure 3 Hypothalamic-pituitary-adrenal Axis Evaluation

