8.2.1.1 Morning Cortisol Test

The morning cortisol test will be done in all participants 4 weeks after reaching the 5 mg dose of OCS, and before further dose reductions. It is also done 3 months after a participant has completed a test indicating complete AI.

Serum samples for cortisol will be collected between 8 and 9 am and will be sent to a central laboratory for evaluation.

The following values will be used to define AI status for the morning cortisol test:

Table 9 Cortisol Status

AI status	SI units	Participants taking oestrogen- containing contraceptives
Normal	>350 nmol/L	>700 nmol/L
Indeterminate results	100 - 350 nmol/L	200 - 700 nmol/L
Complete AI	<100 nmol/L	<200 nmol/L

Once the results are available, the site will inform the participant of the results via telephone. For sites where tetracosactides are available, and depending on the result, the actions that will be implemented are as follows:

- If cortisol levels are within normal range and the participant does not exhibit any signs and/or symptoms of AI, the participant will continue OCS down-titration by 2.5 mg Q4W
- If cortisol levels are within normal range but the participant exhibits signs and/or symptoms of AI, then OCS down-titration should continue at a slower pace (1 mg Q4W).
- If cortisol levels are below the normal range and above the complete AI range (indeterminate result), then the participant will be instructed to maintain the current OCS dose and come back to the site within 1 week for an ACTH stimulation test (Section 8.2.1.2)
- If complete AI is confirmed, sites will inform participant that the OCS dose will remain the same without further reduction until there is evidence of recovery from the complete AI without worsening of asthma control. The morning cortisol test and associated clinical assessments (see Table 1) will be repeated 3 months later. After the repeat morning cortisol test, the site will inform the participant based on the results as follows:
 - If morning cortisol results indicate normal cortisol values, then reductions will be 2.5 mg Q4W, and the participant would subsequently move to maintenance at the OCS lowest possible dose
 - If morning cortisol results are indeterminate, then reductions will be delayed further, and the participant would return approximately 1 week later for an ACTH stimulation test:
 - o If normal result after ACTH stimulation (Table 10): reduce by 2.5 mg Q4W then move to maintenance at the lowest possible dose

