8.2.1.2 Adrenocorticotropic Hormone Stimulation Test

The tetracosactide (also known as Synacthen, Cortrosyn, or cosyntropin) ACTH stimulation test will be performed when morning cortisol levels are in the indeterminate range (for sites

where tetracosactide is not available or not registered, please see Appendix M).

Options for sourcing tetracosactide are provided below:

- Acquire Synacthen or Cortrosyn 250 mg for intravenous (IV) or intramuscular (IM) injection locally and submit invoices for reimbursement (preferred option, if possible).
- If the medication is available in your country but the site cannot directly acquire the medications, then Labcorp or AstraZeneca may arrange for delivery to the site.
- If the medication is available in your country, but delivery to the site is delayed, the site may request permission from Labcorp to use the alternative method described in Appendix M.
- Sites in countries where the medications are not registered must use the alternative method in Appendix M.

The following values will be used to define AI status for the ACTH stimulation test:

Table 10 ACTH Stimulation Status

AI status	SI units	Participants taking oestrogen- containing contraceptives
Normal	>450 nmol/L	>675 nmol/L
Indeterminate results	250 - 450 nmol/L	375 - 675 nmol/L
Complete AI	<250 nmol/L	<375 nmol/L

The sites will inform the participant of the morning cortisol results via phone call, and a visit will be scheduled within 1 week for the ACTH stimulation test.

An injection of the fast-acting ACTH stimulant will be given IV or IM. Serum samples for cortisol will be collected between 8 and 9 am and will be sent to a central laboratory for evaluation as follows: a blood sample for serum cortisol will be collected at 0 minutes (before IV or IM injection) and 30 minutes after the IV or IM injection. Peak cortisol response at 30 minutes will be selected to assess AI, and the OCS taper will follow the applicable scenario below:

• If a normal peak cortisol level is demonstrated at 30 minutes, the site will inform the participant via phone call, and the participant will continue OCS dose titration by 2.5 mg Q4W aiming for 0, and subsequently would move to maintenance at the lowest possible OCS dose

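### Protocol Section 7.1 lets Option 2 participants keep tapering OCS but leaves those with an adrenal test outstanding no permitted route to that test

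*Protocol*

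**What the plan says.** Protocol Section 7.1 offers three follow-up options after premature discontinuation of tezepelumab. Option 2 is monthly telephone contact "while continuing ePRO data collection on the handheld device at home (no further procedure will be performed) until the participant completes" the on-site end-of-treatment visit at Week 52. Shortly afterwards the section says that participants on Option 1 or 2 "are allowed to further reduce their OCS dose following the same protocol-specified OCS dose reductions scheme as participants being still on-treatment".

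The scheme referred to is in Sections 8.1.2 and 8.2.1:

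- Section 8.1.2: "The OCS dose titration in the reduction phase will be followed as per Table 7 depending on the initial OCS dose and HPA axis evaluation". In Table 7 every entry for going from 5 mg to 0 mg is conditional on adrenal status.
- Section 8.2.1: "For all participants, HPA axis integrity will be evaluated after 4 weeks on 5 mg/day and prior to tapering down the OCS dose".
- Section 8.2.1.1, on the first test: "Serum samples for cortisol will be collected between 8 and 9 am and will be sent to a central laboratory for evaluation".
- Section 8.2.1.2, on the test that follows an indeterminate result: "An injection of the fast-acting ACTH stimulant will be given IV or IM". Blood is drawn before the injection and 30 minutes after it. Where tetracosactide cannot be used, Appendix M substitutes a second morning cortisol about a week later.
- Table 3 and Section 8.2.1.2: the cortisol test is repeated after 2 months for partial adrenal insufficiency (AI) and after 3 months for complete AI.

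Section 8.1.2 also allows dose reductions to be made remotely, for instance by telephone.

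**The concern.** Read together, the two statements in Section 7.1 permit a taper and rule out the blood tests on which its last part depends. A site with an Option 2 participant who has been on 5 mg/day for four weeks could reasonably do any of three things: continue the taper by telephone without the test, hold the dose, or bring the participant in for sampling despite the bar.

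Two things are at stake. The first is a safety safeguard. Section 2.1 says that withdrawal of OCS leads to "adrenal insufficiency (AI) in approximately 50% of patients", that the impaired stress response can be life-threatening, and that screening for AI during down-titration is important. Under Option 2 the weekly ACQ-6 continues at home, so asthma monitoring survives; the adrenal check has no stated route.

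The second is the primary estimate. Stopping tezepelumab is handled by treatment policy, so doses after discontinuation count. Whether such a participant can be classed as having discontinued OCS may then depend on how the site reads Section 7.1 rather than on asthma control.

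**Working it through.** No figure in the plan depends on this point, so the check sets the texts side by side, then looks at timing and at the endpoints.

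**1. Is there another route to the test under Option 2?**

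| Possible route | What the protocol says | Does it help? |
|---|---|---|
| Telephone calls | Section 7.1 lists safety events, medication changes and exacerbations as the key items | No cortisol or AI item |
| Scheduled assessments | Section 7.1 gives the full Schedule of Activities to Option 1 | Not to Option 2 |
| Week 52 visit | Sections 1.1 and 4.1 stop down-titration from Week 48 | Too late to guide a reduction |
| Visit at which the option is chosen | The conditional cortisol and ACTH rows are tied to reaching 5 mg and, as far as the table can be read, carry no mark for this visit | At best, those already due a test then |
| Express exception for adrenal testing | None found | No |
| Express limit on the Option 2 taper | None found | No |

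**2. Who is affected?** Option 2 participants with a first, confirmatory or repeat test still due. Those already tested normal need no repeat. Participants above 5 mg/day can taper as far as 5 mg/day without a test. Option 3 is not in the taper permission.

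**3. When does the first test fall due?** Inputs are the Table 7 steps, first reduction at Week 4, no interruption, and a test 4 weeks after reaching 5 mg/day (or at Week 4 if baseline is 5 mg). Table 7 can be read in two ways: the interval is set by the dose being left, or by the step just taken. Example for baseline 20 mg: 15 mg at Week 4, 10 mg at Week 6, 7.5 mg at Week 8, 5 mg at Week 12 or Week 10, so the test is at Week 16 or Week 14.

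| Baseline dose | First test due | Earliest 0 mg if normal (2.5 mg at the test, 0 mg 4 weeks later) |
|---|---|---|
| 5 mg | Week 4 | Week 8 |
| 7.5 mg | Week 8 | Week 12 |
| 10 mg | Weeks 10–12 | Weeks 14–16 |
| 20 mg | Weeks 14–16 | Weeks 18–20 |
| 30 mg | Weeks 16–19 | Weeks 20–23 |
| 40 mg | Weeks 18–21 | Weeks 22–25 |

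A participant who enters Option 2 before the relevant week has not had the test. Exacerbations, deteriorations and repeat tests lengthen that period. All these weeks precede Week 48, so the conflict falls while tapering is allowed. On an uninterrupted taper they also precede Week 28, so both primary timepoints can be touched.

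**4. Effect on the primary endpoints.** The final dose is the last reported dose that was stable for at least 2 weeks (Protocol Table 13, SAP Table 4). Take a participant with asthma control maintained:

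- Held at 5 mg/day: not a success for discontinuation; a success for ≤ 5 mg/day.
- Tapered to 0 mg: a success for both.

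The difference per participant is 1/300 = 0.33 percentage points for discontinuation and zero for ≤ 5 mg/day. The planned 95% CI half-width at 50% and n = 300 is 5.8 points, so a shift of that size would need 0.058 × 300 ≈ 17 participants classified differently. The supplementary analysis in SAP Section 4.2.1.6 fixes the dose at the time of discontinuation and is little exposed.

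**The case against.** The strongest reply is that no contradiction need arise in practice. Section 7.1 allows the taper; it does not require it. The permission is tied to following the same scheme, and under Table 7 an untested step below 5 mg/day is not that scheme. A site that holds at 5 mg/day for want of a test breaches neither sentence. Adrenal evaluation also sits under Section 8.2 as a safety assessment: Section 8 allows unscheduled samples for safety reasons, and Section 8.2.3 allows extra safety samples at the investigator's discretion.

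Much of this stands. A reader might infer that the protocol licenses untested tapering, or that sites cannot comply at all; neither follows. But the general sampling provisions do not expressly override a specific bar, and Section 8 also rules out waivers and exemptions. A permission whose condition cannot be met by any stated route still leaves sites to choose. Nor does holding at 5 mg/day describe someone already below that dose on the 1 mg steps for partial AI, whose 2-month repeat falls due under Option 2.

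A reader might also think that weekly or two-weekly steps have no mechanism when calls are monthly. Section 8.1.2 and Schedule of Activities footnote k already cover remote steps between visits, and nothing bars an extra call. Nor are Option 2 participants the least observed: Option 3 has a single contact at Week 52.

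**Conclusion.** The point holds as a conflict between stated rules on a safety safeguard, limited to Option 2 participants with an adrenal test outstanding. It does not depend on how many there are.

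Its size cannot be derived. The documents give no Option 2 rate, and the number is probably small. SAP Section 4.1.1.2 will report the count by follow-up option, but not who had a test due. If one assumed that 2–5% of 300 chose Option 2 (6–15 participants), a reader might infer a shift of 2–5 points in the discontinuation proportion. That is a ceiling: it needs every one of them to be untested, to reach 5 mg/day with stable asthma, and to reach 0 mg under one reading only. It is not an expected bias.

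A reader might also apply the 50% figure in Section 2.1 to such a count to estimate undetected AI. The documents do not support this. The figure is a general one for OCS withdrawal, not a rate for this population at 5 mg/day, and the sum would assume that all were tapered untested, contrary to Table 7.

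The exposed primary endpoint is the proportion that discontinued OCS, at Week 28 and Week 52. The ≤ 5 mg/day proportion is largely unaffected.

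**What to change.** Reconcile Section 7.1, and the Schedule of Activities footnotes on adrenal testing and dose reduction, with Sections 8.1.2 and 8.2.1. The text should state either whether adrenal evaluation is excepted from the Option 2 bar, or how the taper permission applies to an Option 2 participant whose first, confirmatory or repeat test is outstanding. Which clinical rule to adopt is for the sponsor; this review does not propose one.

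The cost is one or two sentences and a footnote. If testing is excepted, the added burden is at most a few conditional samples that the scheme already requires of tapering participants. For data already collected, a short listing of Option 2 participants with their adrenal test dates and results and their final dose would show how far the estimate is touched, with no change to the planned analyses.

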- ^e For participants who have reached OCS doses equal to 5 mg/day, hypothalamic-pituitary-adrenal (HPA) axis integrity will be assessed at the end of a 4-week period on 5 mg/day using the 8 to 9 am morning cortisol level. If the morning cortisol level is indeterminate, then an ACTH stimulation or alternative method is required within approximately 1 week. For those participants who had a baseline OCS dose equal to 5 mg/day, HPA axis integrity will be assessed 4 weeks after first dose of tezepelumab administration and before initiation of the OCS reduction and maintenance phase.
- ^f For sites where no tetracosactide is available/registered, an alternative method to identify adrenal insufficiency is provided (see Appendix M).
- g Only events that fall into the following categories are collected in this study: SAEs, DAEs, and AESIs. AEs of special interest in this study fall into the following categories: serious hypersensitivity reactions (see Appendix G), serious infections (including serious opportunistic infections), helminth infections, serious cardiac events, malignancy, Guillain Barre syndrome, and adrenal crisis.
- hAt Visit 2, assessment should be performed before any other study procedures. After Visit 2, any available PROs which have not been completed prior to the site visit, should be completed at the site prior to any other study procedure.
- ⁱ The ACQ-6 will be completed every 1 week at home on the handheld device.
- AQLQ(s)+12, SGRQ, SNOT-22 and PPOCS are to be completed at home as per Schedule of Activities (within a defined window of ± 2 days; this defined window may or may not coincide with the on-site visit).
- k Oral corticosteroid dose reduction is for participants who have not reached the lowest possible stable dose, and who have not lost asthma control. No further OCS dose reduction will be allowed from Week 48 onwards. Note that for participants who must reduce OCS dose more frequently than every 4 weeks or between site visits (see reduction scheme in Table 7), OCS dose reduction may occur remotely (eg, by telephone) instead of a clinic visit.
- Oral corticosteroid dose reduction not allowed at Week 48.
- ^m For participants who prematurely discontinue study drug and do not want to undergo further study assessments, apart from phone call 52 weeks after baseline (see Section 7.1).
 - ⁿ At Visit 2, all assessments should be done before tezepelumab administration to ensure proper calculation of baseline values.

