7 DISCONTINUATION OF STUDY INTERVENTION AND PARTICIPANT DISCONTINUATION/WITHDRAWAL

7.1 Discontinuation of Study Intervention

It may be necessary for a participant to permanently discontinue (definitive discontinuation) tezepelumab.

Reasons for discontinuation of study intervention may include:

- Participant decision: The participant is at any time free to discontinue treatment, without prejudice to further treatment.
- Incorrectly enrolled/dosed participant in whom the inclusion/exclusion criteria violation would put the participant at undue risk.
- Adverse event for which the investigator judges continued treatment may put the participant at undue risk.
- Severe noncompliance with the Clinical Study Protocol (CSP).
- Pregnancy (see Section 8.3.11).
- Development of any study specific criteria for discontinuation, including:
 - An anaphylactic reaction to the IP requiring administration of epinephrine
 - A helminth parasitic infestation not responding to anti-helminth treatment
 - Any malignancy except participants who develop basal cell carcinoma or localised squamous cell carcinoma of the skin, provided that the malignancy is excised and determined to have clean margins.
- Development of one or more of the following:
 - Confirmed alanine aminotransferase (ALT) or aspartate aminotransferase
 (AST) increase of ≥ 8 × ULN
 - Confirmed ALT or AST increase of \geq 5 × ULN for more than 2 weeks
 - Confirmed ALT or AST increase of ≥ 3 × ULN and total bilirubin of ≥ 2 × ULN
 - ALT or AST of $\geq 3 \times$ ULN with the appearance of fatigue, nausea, vomiting, right upper quadrant pain or tenderness, fever, rash, and/or eosinophilia ($\geq 5\%$).

For discontinuation pertaining to COVID-19, please see Appendix C.

A participant who decides to discontinue study drug will always be asked about the reason(s)

and the presence of any AEs. The reason for premature discontinuation of tezepelumab should be documented in the source documentation and recorded in the eCRF.

All participants who prematurely discontinue study drug should:

- return to the study site and complete the procedures described for the IPD Visit within 4 weeks (± 7 days) after last tezepelumab administration,
- and have a follow-up visit 16 weeks after last tezepelumab administration (± 5 days) (see Table 1, Visit 16).

Participants who discontinue treatment should be encouraged to return for all regularly scheduled visits for safety and efficacy assessments.

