8.3.1 Time Period and Frequency for Collecting AE and SAE Information

SAEs, DAEs, and AESIs will be collected from time of signature of informed consent throughout the treatment period and including the follow-up period (16 weeks after the last dose of IP).

If the investigator becomes aware of an SAE with a suspected causal relationship to the IP that occurs after the end of the clinical study in a participant treated by him or her, the investigator shall, without undue delay, report the SAE to the sponsor.

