3.3.1 General Study Level Definitions

3.3.1.1 Study period definition

Efficacy analyses are based on planned treatment period, unless otherwise specified. Safety analyses are based on-treatment and/or on-study period.

- Planned treatment period: starts on the date of first dose of IP and ends on the date of the Visit 15 (Week 52) visit or earlier study withdrawal date.
- On-treatment period: starts on date of first dose of IP and ends on earliest(date of last dose of IP + 33 days, date of death, date of study withdrawal). The date of study withdrawal is the completion or discontinuation date from the DISPOSITION eCRF page, where any participant status other than "Completed" has been entered.
- On-study period (planned treatment period and follow-up): starts on the date of first dose of IP and ends on the study completion or withdrawal date.

For analysis performed at primary database lock, the planned treatment period is understood to include all data recorded starting on the date of first dose of IP up until the date of the data cut-off for the primary database lock (details regarding the DCO date and data cleaning can be found in Data Cleaning Requirements for Primary Analysis Lock Plan).

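### For option 3 participants whose last dose falls at Weeks 0 to 32, Protocol Section 7.1 both schedules and excludes the safety contact 16 weeks after the last dose

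*Protocol*

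**What the plan says.** Protocol Section 7.1 opens its follow-up rules with "All participants who prematurely discontinue study drug should" and lists two items. The first is to "return to the study site and complete the procedures described for the IPD Visit within 4 weeks (± 7 days) after last tezepelumab administration". The second is to "have a follow-up visit 16 weeks after last tezepelumab administration", identified as Visit 16. Neither item exempts any group.

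The section then describes three follow-up options, offered at the IPD visit. Option 3 is a single telephone contact 52 weeks after baseline, followed by: "No other study assessments will be performed prior to this contact". The section also says that calls under options 2 and 3 collect SAEs, DAEs and AESIs, changes in concomitant medication, and exacerbation information.

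Footnote m of the Schedule of Activities (Section 1.3), which concerns return of the ePRO device, describes the same group as those who "do not want to undergo further study assessments, apart from phone call 52 weeks after baseline". It names no 16-week contact. SAP Section 4.1.1.2 likewise describes option 3 only as a Week 52 contact.

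Protocol Section 8.3.1 has SAEs, DAEs and AESIs collected "throughout the treatment period and including the follow-up period (16 weeks after the last dose of IP"). The Schedule of Activities marks the SAE/DAE/AESI assessment at both the IPD visit and Visit 16. In SAP Section 3.3.1.1 the on-study period "starts on the date of first dose of IP and ends on the study completion or withdrawal date"; the on-treatment period ends no later than 33 days after the last dose.

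**The concern.** Two instructions in one section give a site opposite directions for the same participant. The contact in dispute is the one that closes the protocol's own post-dose safety period. If option 3 is taken at its word, the last scheduled safety question inside that period comes at the IPD visit, about 4 weeks after the last dose. Anything that happens between then and week 16 is first asked about at the Week 52 call, from memory.

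SAEs, DAEs and AESIs are the only adverse events this study collects, so this part of the safety record has no other adverse-event data to support it. Sites may also resolve the conflict differently. The timing and completeness of ascertainment among option 3 participants would then depend on which sentence a site happened to follow.

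**Working it through.** **Inputs**
- Dosing every 4 weeks from Week 0 to Week 48, 13 doses (Protocol Section 1.1).
- IPD visit at 4 weeks (± 7 days) after the last dose, and Visit 16 at 16 weeks (± 5 days) after it (Section 7.1).
- Option 3 call at Week 52 (Section 7.1).
- SAE/DAE/AESI collection to 16 weeks after the last dose (Section 8.3.1).
- On-treatment period to last dose + 33 days (SAP Section 3.3.1.1).

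**The plan's own figures.** For a participant who receives every dose, 48 + 16 = 64, which agrees with the stated Week 64 follow-up. Also 52 − 16 = 36, which agrees with the Week 36 cut-off used in Section 7.1.

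**When the instructions conflict.** With last dose at Week w, the IPD visit is at w + 4 and Visit 16 at w + 16. Visit 16 falls before the Week 52 call when w + 16 < 52, that is w < 36. On the 4-weekly schedule this means w = 0, 4, …, 32, or 9 of 13 dosing times. At w = 36 the two contacts coincide. For later last doses Visit 16 comes after Week 52, which the option 3 sentence does not exclude.

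**Delay if option 3 is followed literally.** Delay relative to Visit 16 = 52 − (w + 16) = 36 − w weeks.

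| Last dose (week) | IPD visit | Visit 16 | Delay to Week 52 call (weeks) |
|---|---|---|---|
| 0 | 4 | 16 | 36 |
| 4 | 8 | 20 | 32 |
| 8 | 12 | 24 | 28 |
| 12 | 16 | 28 | 24 |
| 16 | 20 | 32 | 20 |
| 20 | 24 | 36 | 16 |
| 24 | 28 | 40 | 12 |
| 28 | 32 | 44 | 8 |
| 32 | 36 | 48 | 4 |
| 36 | 40 | 52 | 0 |

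These are nominal times. With the ± 5 day window on Visit 16, the w = 0 delay runs from (364 − 117)/7 = 35.3 to (364 − 107)/7 = 36.7 weeks.

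**Which summaries are exposed.** The IPD visit falls on days 21 to 35 after the last dose (28 ± 7). At the nominal day 28 it leaves 33 − 28 = 5 days of the on-treatment period unasked. At the earliest, day 21, it leaves 12 days, and at day 35 none. The on-treatment tables are therefore largely covered. The on-study period continues beyond this, so the on-study SAE and AESI summaries carry most of the effect.

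**The case against.** The strongest reply is that little is lost. The exclusion applies only after the IPD visit, which itself assesses SAEs, DAEs and AESIs. The Week 52 call asks about the same events, so ascertainment is late rather than absent. Unscheduled visits also capture events, and Section 8.3.2 has investigators follow unresolved events for as long as medically indicated, although without further eCRF recording. Section 7.1 says participants *should* have the 16-week follow-up, which is softer than a requirement. Option 3 exists for people unwilling to do more, and people who refuse all contact leave the study, so keeping the burden low is a reasonable retention choice. All of this stands, and it limits the size of the problem.

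One could also argue that Visit 16 is not a study assessment and so escapes the exclusion. The Schedule of Activities undercuts that, because it marks the SAE/DAE/AESI assessment at that visit.

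Some stronger readings are tempting, but the documents do not support them:
- **A 48-week safety gap.** From IPD to Week 52 is 48 weeks only if the Week 0 dose alone was given and option 3 overrides Visit 16. Of those 48 weeks, 36 lie after the 16-week collection period has ended.
- **Twelve of the 16 post-dose weeks left uncovered.** Completers have the same pattern (last dose Week 48, visit Week 52, call Week 64), and restoring Visit 16 would not change it. What changes is how soon the question is asked.
- **Early stoppers as mainly adverse-event cases.** Adverse events are one of several listed reasons, and no frequency is given.
- **A particular adrenal-crisis risk under option 3.** Section 7.1 permits continued protocol OCS reduction after stopping for options 1 and 2 only, so this should not be assumed.
- **A reverse conflict for options 1 and 2**, in which Section 8.3.1 stops collection before their Week 52 contacts. This disappears if the treatment period in 8.3.1 means the planned 52-week period, as Protocol Section 9.4.1 and SAP Section 3.3.1.1 allow.

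**Conclusion.** The contradiction is real and limited. It concerns option 3 participants whose last dose was at Weeks 0 to 32. For them, following option 3 literally removes the contact that closes the Section 8.3.1 collection period and postpones the question about weeks 4 to 16 after the last dose by 36 − w weeks, at most 36 and at least 4. This assumes nominal visit times and a site that lets the option 3 sentence govern. If the site keeps Visit 16, there is no delay. A reader might infer that these events go uncollected; they do not, because the Week 52 call asks for them.

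The effect on the reported results cannot be sized, because the documents do not say how many participants are expected to choose option 3 or when they would stop. The on-study SAE and AESI summaries are the place to look for it. No efficacy analysis depends on this point.

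**What to change.** Reconcile the two parts of Section 7.1 and footnote m of the Schedule of Activities. In option 3 and in footnote m, state that no other assessment is performed before Week 52 except the Visit 16 telephone contact 16 weeks after the last dose. Section 7.1 already specifies that contact for all who stop early, so no new procedure is created. The short description of option 3 in SAP Section 4.1.1.2 can be brought into line at the same time.

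The cost is a small wording amendment and one short call per affected participant. Some will decline it, since option 3 is for people who want minimal contact; the wording should allow for that without treating a refusal as study withdrawal.

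Optionally, Section 8.3.1 could say that its treatment period is the planned 52-week period, so that it reads the same way as the SAP on-study period. That is a clarification only.
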